7.2 Procedures and Assessments

7.2.1 Schedule of Assessments

All assessments of the investigation will be conducted as indicated in the following table which displays the frequency and timing of all measurements.

Table 1. Data collection schedule

	Inclusion Intermediate Ad		Additional	Final visit	Early Termination
	visit	visit	visits*	Final visit	visit**
Visit name (corresponding day)	V1 (D0)	V2 (D3±2)	Between V2 and V3	V3 (D21+2 or earlier, as soon as the wound is epithelialized completely)	ET
Oral consent of the patient to	X				
participate					
Inclusion/exclusion criteria	\boxtimes				
Randomization	X				
Demographics	X				
Medical history	X				
Wound/surrounding skin characteristics	×	×	×	X	X
Investigational product application	×	×	×		
Secondary dressing / fixation use	×	×	×		
Dressing removal (to follow the standardized removal procedure)		X	×	X	X
Intake of analgesics	X	×		×	×
Pain assessment (VAS) after application of investigational product	×				
Pain assessment (VAS) during removal		\boxtimes			

Version 2.0 – March 29, 2019

Amount of exudate	X	X	×	X	X
Wound shift (ratio necrotic/ fibrinous/ granulation/ epithelisation tissue)	×	×		X	X
Complete healing assessment		×	×	×	×
Wound photograph	×	×		×	×
Photograph of the investigational product on the wound***	×	×		X	×
Adverse events/Adverse device effects	×	×		×	×
Global dressing investigator evaluation		×		×	×
Global dressing subject's evaluation				X	×
Concomitant treatment	×	X		×	X

^{*} optional, if required by wound's condition

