7.2.2 Investigation Procedures

7.2.2.1 Inclusion visit (V1, D0)

At the inclusion visit (V1, D0) the subject will receive complete information related to the investigation. Prior to any assessment, the oral consent of the patient to participate, according to the "Etudes interventionnelles à risques minimes" French regulations, will have to be obtained by the investigator. Inclusion and exclusion criteria will be checked by the investigator.

The subject will be consecutively allocated to a subject code providing they fulfil all inclusion and none of the exclusion criteria. The subject will be randomized to either receive Lomatuell Pro® or UrgoTul®.

The investigator will report the date of visit, and collect subject information in the case report form (CRF) such as demographic characteristics (gender, age, height, weight), significant medical history including the presence and type of disease which could interfere with the evolution of healing, concomitant therapy, intake of analgesics, characteristics of wound (type and duration of the wound, location, size, assessment of the wound bed (bleeding, maceration, inflammation, infection, ratio necrotic/ fibrinous/ granulation/ epithelisation tissue, and tissue in-growth in the dressing holes) and condition of the surrounding skin (inflammatory signs, irritation, allergic rash/eczema, blistering, skin stripping, maceration, dry, trauma to wound edges, product degradation on the skin, hematoma). Assessment of the amount of exudate (drainage) will be performed after removal of the dressing and before wound cleansing and it will be categorized as none, light, moderate, or heavy.

If applicable, the previous treatment or dressing used will be reported in the CRF. The investigator will also interview the subject about the use of analgesics since the wound occurrence including the frequency of use. These data will be reported in the appropriate form of the CRF.

The wound (with a millimetre ruler) will be photographed by the investigator before the first investigational product application according to the photography guidelines (see Appendix

^{**} will be performed for the patients who discontinued the study preliminary for any reason, instead of the visit V3

^{***}after application of the product at V1, before removal of the product and after application of a new product at V2, before removal of the product at V3 or Early termination visit

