7.6 Concomitant Treatment

All medication which is considered necessary for the subject's safety and well-being may be given at the discretion of the investigator.

All concomitant medication and relevant treatment must be recorded in the appropriate section of the Case Report Form (CRF).

For analgesic treatment all data including type of analgesic, frequency of use before wound treatment (at D0 only) and hour of intake before dressing removal must be recorded in the appropriate form of the CRF.

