7.9.1.2 Efficacy analyses

Analysis of the main criterion

The test for the non-inferiority of Lomatuell Pro® vs UrgoTul® for the main criterion will be carried out through a confidence interval (CI) approach. Non-inferiority will be established if the lower unilateral limit of the 97.5% CI in the PP population for the between-treatment difference (Lomatuell Pro® - UrgoTul®) in the percentage of wound dressing associated with a pain < 30 mm on VAS at V2 does not exceed -10%.

Considering that the studied population is "patients with an acute wound" and that the primary endpoint will be assessed at V2 (Day 3±2); we can expect very few drop-outs. We also expect few patients with a major protocol deviation. Therefore, we can conclude that an assumption of 10% attrition rate is acceptable for this study.

In order to unambiguously conclude to non-inferiority in agreement with most of guidelines, the same analysis will be performed on the mITT population. In case of missing data to evaluate the primary criterion, the subjects will be considered as failures. The trial will be considered positive if both approaches support noninferiority.

Adjustment

The frequency of analgesic intake will also be analysed. In case of a significant difference between the 2 dressing groups, the analysis of the primary criterion (painless dressing removals) will be adjusted using a Mantel-Haenszel test.

Analysis of the secondary criteria

The following statistical tests will be used to analyse the secondary criteria according to the criteria type:

- Qualitative nominal criteria will be compared using a Chi² test.
- Qualitative ordinal criteria will be compared using a Mann-Whitney-Wilcoxon test
- Quantitative criteria will be compared using an analysis of variance (ANOVA)

Degree of significance

The criteria for which the degree of significance of the bilateral test will not exceed 0.05 (statistically significant difference) will highlight the specificities between the 2 groups of dressing.

Percentage of complete healing at V3

A wound will be considered as completely healed when there is 100% of epithelialization (first epithelia layer) of the wound. The percentage of wounds healed will be calculated based on a blind assessment from photographs using W.H.A.T.

Assessment of the wound condition

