The wound bed condition will be evaluated at V1, V2 and V3 or ET regarding 6 condition items - bleeding, maceration, inflammation, infection, ratio necrotic/ fibrinous/ granulation/ epithelisation tissue, and tissue in-growth in the dressing holes by means of the following 4-points scale: *none*, *mild*, *moderate*, *severe*. The percentage of each modality for each condition items will be calculated.

Assessment of the surrounding skin condition

The condition of the surrounding skin will be assessed at V1, V2 and V3 or ET regarding different conditions: inflammatory signs, irritation, allergic rash/eczema, blistering, skin stripping, maceration, dry, trauma to wound edges, product degradation on the skin, hematoma, other. These condition items will be assessed by means of the scale *Yes/No*. The percentage of each modality will be calculated.

Wound closure according to inclusion wound exudation status.

This will use a Cochran-Mantel-Haenszel test including treatment groups and baseline wound exudation status (none, light and moderate/heavy).

Global assessment of the dressing by the investigator

The global assessment of the dressing will be performed by the investigator at V2 and V3 or ET. Each item will be evaluated by means of the following scale: *very good, good, poor, and very poor*.

The percentage of each modality of each criterion (ease of handling, ability to maintain its integrity, ease of application, ability to be repositioned during application, conformability, wound adhesion, ability of dressings to stay in place, transparency, ability to transfer wound fluid to the secondary dressing, ease / speed of removal, overall impression, and absence of residue) will be calculated.

Global assessment of the dressing by the subject

A global assessment of the dressing will be performed by the subject at V3 or ET. Each item (ability to maintain its integrity, ability of dressings to stay in place, transparency, comfort of the patient, ability to transfer wound fluid to the secondary dressing, ease/speed of removal, overall impression) will be evaluated by means of the following scale: *very good, good, moderate, poor, very poor.* The percentage of each modality will be presented.

Assessments from the study nurse's booklet at each dressing change

The total number of dressing changes will be calculated and the mean value of dressing changes will be calculated.

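### The planned analgesic adjustment of the primary analysis is a Mantel-Haenszel test, which gives no limit to set against -10%; its estimator, strata, visit and role are not stated

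*Protocol*

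**What the plan says.** All of this is in Protocol 7.9.1.2 unless stated.

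- **Decision rule.** "Non-inferiority will be established if the lower unilateral limit of the 97.5% CI in the PP population" for Lomatuell Pro minus UrgoTul does not fall below -10%. The same analysis is run in mITT with missing outcomes counted as failures. "The trial will be considered positive if both approaches support noninferiority".
- **Adjustment.** "The frequency of analgesic intake will also be analysed". If the dressing groups differ significantly, "the analysis of the primary criterion (painless dressing removals) will be adjusted using a Mantel-Haenszel test". The paragraph ends there.
- **Contrast.** For wound closure by exudation status, a secondary analysis, the strata are named: "This will use a Cochran-Mantel-Haenszel test including treatment groups and baseline wound exudation status (none, light and moderate/heavy".
- **Analgesic data.** The schedule in Protocol 7.2.1 has a row "Intake of analgesics" ticked at V1, V2, V3 and early termination. Protocol 7.2.2.1 has the investigator "interview the subject about the use of analgesics since the wound occurrence including the frequency of use". Protocol 7.6 requires that type, "frequency of use before wound treatment (at D0 only) and hour of intake before dressing removal must be recorded".
- **SAP.** Section 4 says that it is based on the Suprasorb C protocol. Section 7.2 plans no formal comparison. It does not mention this adjustment.

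**The concern.** The primary question is whether the shortfall could be as large as 10 points. A Mantel-Haenszel test asks whether there is any association at all after stratification. Its p-value cannot be set against -10%, so once the trigger fires, the plan has no adjusted result on the scale of its own decision rule.

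Several choices are also left open: which visit's intake fires the trigger and forms the strata, how many strata there are, whether the adjustment applies to PP, mITT or both, and whether the adjusted result replaces or supports the unadjusted one. The visit matters most. Use before treatment, asked at D0, is a pre-treatment covariate. Intake before the V2 removal comes after randomisation in an open-label trial and may itself respond to the dressing, so stratifying on it could remove part of the effect under test.

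At stake is an adjusted p-value for the primary endpoint with no pre-stated reading, and a choice of covariate that could be made after the data are seen.

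**Working it through.** **1. The plan's own figure.** Inputs from Protocol 7.9.2: 95% painless (taken as the rate in both arms), margin 10 points, one-sided 2.5%, power 80%, attrition 10%.

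n = (1.960 + 0.842)² × 2 × 0.95 × 0.05 / 0.10² = 74.6, so 75 per group; 75/0.9 = 83.3, so 84. Both match. The sample size therefore rests on a risk difference and its limit, not on an equality test. Expected failures are 0.05 × 75 = 3.75, about four per arm.

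**2. Two constructed trials.** All counts are assumed: 75 per group, D0 analgesic use 15/75 v 30/75 (Lomatuell Pro first). Trigger: z = 0.20/√(0.30 × 0.70 × 2/75) = 2.67, p = 0.0075, so it fires. The protocol does not name the interval method. I use Wald for the unadjusted limit, with the same unpooled variance that reproduces the sample size.

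Painless removals:

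| | Non-users | Users | Total |
|---|---|---|---|
| Trial A | 59/60 v 44/45 | 12/15 v 28/30 | 71/75 v 72/75 |
| Trial B | 58/60 v 44/45 | 14/15 v 30/30 | 72/75 v 74/75 |

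Formulas, with a of n1 painless on Lomatuell Pro and c of n0 on UrgoTul in a stratum of size N, and m = a + c:

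- Test: χ² = [Σ(a − n1·m/N)]² / Σ[n1·n0·m(N − m)/(N²(N − 1))], no continuity correction.
- Weighted difference: d = Σw(a/n1 − c/n0)/W, with w = n1·n0/N and W = Σw.
- Sato variance: (d·P + Q)/W², with P = Σ[n1²c − n0²a + n1·n0(n0 − n1)/2]/N² and Q = Σ[a(n0 − c) + c(n1 − a)]/(2N).

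In both trials W = 60×45/105 + 15×30/45 = 25.71 + 10 = 35.71.

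*Trial A.*
- χ² = (0.143 − 1.333)²/(0.485 + 1.010) = 0.948, p = 0.330.
- d = (0.143 − 1.333)/35.71 = -3.33 points.
- P = 1.138, Q = 1.690, SE = √(−0.0333 × 1.138 + 1.690)/35.71 = 3.60 points.
- Limit = -3.33 − 1.96 × 3.60 = -10.39. **Margin missed.**

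*Trial B.*
- χ² = (−0.286 − 0.667)²/(0.721 + 0.222) = 0.962, p = 0.327.
- d = (−0.286 − 0.667)/35.71 = -2.67 points.
- P = 0.655, Q = 1.029, SE = √(−0.0267 × 0.655 + 1.029)/35.71 = 2.82 points.
- Limit = -2.67 − 1.96 × 2.82 = -8.18 (working from unrounded values). **Margin met.**

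With stratum binomial variances the limits are -10.64 and -8.39, so the answers do not change. Unadjusted, both trials pass: -1.33 with limit -8.08, and -2.67 with limit -7.81. The two tests give the same p-value to two decimals, while the adjusted limits fall on opposite sides of the margin.

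**3. How often it would matter.** Assume that D0 use is the trigger variable, tested at two-sided 5%. Randomisation then makes the trigger a chance event: it fires in 4.8 to 5.5% of trials for D0 use of 10 to 50%. In simulations at a true 95% v 95% (75 per group, 400,000 trials per setting), when the trigger fires the stratified and unadjusted decisions differ in 4.2 to 4.7% of trials if D0 use is not prognostic. If users fail at 10% with 5% failing overall, they differ in 6.4 to 13.9%. Jointly:

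- low end: 0.05 × 0.042 = 0.2% of all trials;
- high end: 0.05 × 0.139 = 0.7% (0.8% if the trigger rate is taken as 5.5%).

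The high end is extreme: at 50% use it puts every failure among users (0.5 × 10% + 0.5 × 0% = 5%).

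If intake before the V2 removal is meant, the 5% need not hold, and the documents give nothing from which to work out another figure.

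**The case against.** **Intent.** The protocol describes the confidence-interval comparison itself as a test, and says that this analysis is what gets adjusted. The Mantel-Haenszel family includes a common risk difference with an interval, so a stratified difference set against -10% may be what was meant. That is plausible, and it is why the repair is short. But only the test is named, so the text does not settle it.

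**Primary decision.** A reader might infer that success becomes undefined once the trigger fires. The documents do not support that: the success sentence ties a positive trial to the confidence-interval rule in PP and mITT and gives the adjusted result no part in it.

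**Non-significance as proof.** A reader might also infer that a non-significant Mantel-Haenszel result would be taken as non-inferiority. That would be serious: at a true 85% v 95%, an unstratified equality test is non-significant in 44.6% of trials while the Wald rule is met in 3.7%. The protocol says nothing of the kind, so these figures do not count towards the size of the problem.

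**Visit.** Protocol 7.6 records frequency at D0 only, which points to D0. However, 7.9.1.2 does not say so, the endpoint is pain at V2, and the hour of intake before removal is recorded there too.

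**Level of detail.** Strata and variance estimators usually belong in an SAP. That is fair, but the one supplied is for another product. The statement that they are undefined therefore rests on the protocol alone.

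**Reach.** The tables in the working are hand-built, and trial A misses the margin by only 0.4 points. This stands: they show possibility, not frequency.

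**Conclusion.** The point holds as a mismatch between method and question. A Mantel-Haenszel test cannot supply an adjusted answer to a question decided by a limit against -10%, and the estimator, strata, visit, analysis set and role are not given. This goes beyond missing detail, because the method that is named does not fit the rule that it is meant to adjust.

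The practical reach is small: about 0.2 to 0.7% of all trials would have differing adjusted and unadjusted decisions. That rests on D0 use as the covariate, two strata, 75 evaluable per group, a true 95% in both arms, and the assumed ranges of use and prognosis. With V2 intake the reach is unknown. The sample size and the stated primary decision are not in error. It should be fixed before the data are seen, chiefly because the repair is cheap and concerns the primary endpoint.

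**What to change.** Amend the Adjustment paragraph of Protocol 7.9.1.2, and carry it into an SAP written for this trial:

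1. The confidence-interval rule in PP and mITT is the sole primary decision.
2. Replace the Mantel-Haenszel test with a Mantel-Haenszel-weighted risk difference and its one-sided 97.5% lower limit (Sato variance) against -10%, in PP and mITT, labelled supportive.
3. Stratify by analgesic use before wound treatment as collected at D0, in few strata. Any v none would suit the roughly four failures expected per arm. State that the item covers use before the first study dressing, because 7.2.2.1 describes the interview after randomisation.
4. Use intake before the V2 removal only in a sensitivity analysis, noting that it is post-randomisation.
5. Preferably, report the adjusted result whether or not the trigger fires. This goes beyond the defect itself, but removes a data-dependent switch.

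The cost is wording and a few tables from items already collected. The supportive analysis loses a little precision: at a true 95% v 95% with 75 per group, the stratified limit meets the margin in 80.6 to 80.7% of trials against 81.7% unadjusted when D0 use is not prognostic, and in about 81 to 82% when it is. The sample size stays at 75 evaluable and 84 enrolled per group, and primary power is unaffected.

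### Wound-bed and surrounding-skin items are compared between arms without their V1 values: no bias, but a diluted contrast and an avoidable loss of precision that may be small or large

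*Protocol*

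**What the plan says.** Protocol section 7.2.2.1 has the investigator record the wound-bed items and the surrounding-skin signs at inclusion. Section 7.9.1.2 repeats both sets over time. For the wound bed: "The wound bed condition will be evaluated at V1, V2 and V3 or ET regarding 6 condition items", each graded on a four-point scale from none to severe. For the skin: "The condition of the surrounding skin will be assessed at V1, V2 and V3 or ET regarding different conditions", each scored Yes or No. The planned summary of the wound-bed items is: "The percentage of each modality for each condition items will be calculated". The skin items get the same kind of summary.

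The between-arm tests are set by type of variable:
- The rule that covers the Yes/No skin signs reads: "Qualitative nominal criteria will be compared using a Chi² test"
- The rule that covers the graded wound-bed items reads: "Qualitative ordinal criteria will be compared using a Mann-Whitney-Wilcoxon test"
- The rule for measured values, of which there are few here, reads: "Quantitative criteria will be compared using an analysis of variance (ANOVA")

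No covariate, change from V1 or new-onset definition is given for these items. Significance is judged item by item: "The criteria for which the degree of significance of the bilateral test will not exceed 0.05" are to be presented as what distinguishes the two dressings.

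A baseline variable enters one secondary analysis in section 7.9.1.2: wound closure is tested by Cochran-Mantel-Haenszel (CMH) with baseline exudation status. Section 6.2 also announces wound condition by moisture status at inclusion and refers to wound shift, but section 7.9.1.2 has no matching analysis of wound condition.

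The SAP in the file is written for another product (SAP section 4) and plans no formal comparison (SAP section 7.2), so it adds nothing here.

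**The concern.** Patients enter with traumatic, burn or surgical wounds at most three days old (section 7.3.1), and V2 may take place the day after V1 (section 7.2.2.2). Hematoma, damage to the wound edge or inflammatory signs can come from the injury itself and still be present when the first study dressing is removed. Comparing V2 percentages alone counts those signs exactly like signs that appeared under the dressing.

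Two things follow. The carried-over signs add the same background to both arms, so the visible difference shrinks and its noise grows. And with many items each judged at 0.05, an arm that happened to start with more of a sign can end with more of it, and this can be reported as a feature of the dressing. The value needed to separate the two is already in the CRF.

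**Working it through.** **The plan's own figure.** The only sample-size statement (section 7.9.2) concerns the primary endpoint: 95% in both arms, margin 10 points, one-sided 2.5%, power 80%. n = (1.960 + 0.842)² × 2 × 0.95 × 0.05 / 0.10² = 74.6, so 75 per group, and 75/0.9 = 83.3, so 84. Both reproduce, and nothing below changes them.

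**Inputs.** From the documents: 84 per arm, 1:1 allocation, two-sided 0.05. Assumed, because the documents give no values: V1 prevalence of the sign (π), proportion of V1 signs persisting to V2 (q), new onset among patients free of the sign at V1 (a = 5% versus b = 20%), and for quantitative outcomes the correlation r between V1 and the later visit.

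**Yes/No sign, one case in full (π = 20%, q = 80%).**
- V2 rates, πq + (1−π) × onset: 0.16 + 0.8 × 0.05 = 20% and 0.16 + 0.8 × 0.20 = 32%. The 15-point difference in onset shows as 12 points, and 0.16/0.32 = half of the V2 signs in the higher-onset arm were there at V1.
- Unadjusted test: pooled rate 0.26, null SE √(2 × 0.26 × 0.74/84) = 0.0677, alternative SE √((0.16 + 0.2176)/84) = 0.0670. Power = Φ((0.12 − 1.96 × 0.0677)/0.0670) = Φ(−0.19), about 43%.
- Stratified by V1 presence: variance = [π × 2q(1−q) + (1−π)(a(1−a) + b(1−b))]/84 = (0.064 + 0.166)/84, SE 0.0523. Power = Φ(0.12/0.0523 − 1.96) = Φ(0.33), about 63%. Simulating the CMH test gives 62%.

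**Range (simulation, 84 per arm, onset 5% versus 20%; repeat runs agree to about a point).**

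| Present at V1 | Persisting to V2 | Chi², V1 ignored | CMH stratified by V1 |
|---|---|---|---|
| 30% | 85% | 30% | 53% |
| 20% | 80% | 43% | 62% |
| 30% | 50% | 36% | 42% |
| 10% | 50% | 67% | 72% |
| 0% | – | 87% | 87% |

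With equal onset in both arms, both tests reject in about 5% of runs.

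**Chance imbalance at V1.** SD of the between-arm difference = √(2π(1−π)/84): 6.2 points at π = 20% and 7.1 points at π = 30%, giving 95% ranges of about ±12 and ±14 points.

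**Quantitative outcome with a V1 value.** Adjusting by ANCOVA multiplies the residual variance by 1 − r². For a 0.3 SD effect the noncentrality is 0.3 × √(84/2) = 1.94 unadjusted, which gives 49% power. Dividing by √(1 − r²):

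| r | Reduction in SE | Power |
|---|---|---|
| 0.2 | 2.0% | 51% |
| 0.3 | 4.6% | 53% |
| 0.5 | 13.4% | 61% |
| 0.7 | 28.6% | 77% |

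**The case against.** The strongest reply is that nothing is invalid. Randomisation balances V1 signs in expectation, the unadjusted tests keep their error rate, and these are supportive criteria. That stands. A reader might infer that the plan favours one dressing or produces false positives at more than the nominal rate; neither the text nor the simulation supports this.

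A reader might also infer that much of the available precision is lost. That is only the favourable end of an assumed range. When few patients have the sign at V1, or it fades quickly, the gain is a few points or none. The illustration runs from V1 to V2; by V3, at day 21 or at epithelialisation, persistence would plausibly be lower.

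A third tempting reading is that wound area is compared without its entry value, although entry size may run from 3 to 24 cm². W.H.A.T. measures area, but sections 7.8.2.2 and 7.9.1.2 list no area comparison, so there is none to criticise.

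Other replies stand in part:
- The ANOVA rule governs few outcomes here, since the skin items are Yes/No and the wound-bed items ordinal. The Chi² and Wilcoxon rules carry most of the point.
- V1 is not ignored everywhere: wound closure is stratified by exudation. That is not the item's own V1 value, however.
- V1 percentages by arm would probably be tabulated, so an imbalance could be seen. Seeing it does not adjust for it.
- Some items have little or no V1 information: infected wounds are excluded at entry, and in-growth or product residue at V1 presupposes an earlier dressing.
- Section 6.2 asks for wound condition at study end, which is status rather than new onset. Adjustment for V1 still sharpens a comparison of status.
- This trial's own SAP is not in the file and might settle the matter, so the point concerns the protocol as written.

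**Conclusion.** The point holds as a matter of efficiency and interpretation, not validity. For wound-bed and skin items with an informative V1 value, the stated tests leave that value unused, mix signs from the injury with signs arising under the dressing, and leave a chance V1 difference (SD about 6 to 7 points at 20–30% prevalence) open to being reported as a dressing property.

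Under the assumed scenarios the gain in power from using V1 runs from nothing to about 23 points for a Yes/No sign. For a quantitative outcome with a 0.3 SD effect it runs from about 2 points (r = 0.2) to 28 points (r = 0.7). Which end applies cannot be known from the documents. The change is worth making because it is inexpensive, not because a large loss has been shown.

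**What to change.** In section 7.9.1.2, state for each V2 and V3/ET comparison how V1 enters:
- **Yes/No skin items:** CMH test stratified by presence of the sign at V1, with the stratified risk difference and 95% CI. Also report, by arm, new onset among patients free of the sign at V1.
- **Ordinal wound-bed items:** van Elteren test stratified by V1 grade, or a proportional-odds model with V1 grade as covariate, with the adjusted effect and 95% CI. Fix in advance how sparse grades are merged.
- **Any quantitative outcome also measured at V1:** ANCOVA with the V1 value as covariate, giving the adjusted difference and 95% CI.
- **Items with no meaningful V1 value** (for example infection, in-growth into the dressing, product degradation, number of dressing changes): keep the stated tests, and list these items.

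The cost is protocol or SAP wording and slightly more programming. No additional data or visits are required, and the primary analysis and sample size stay as they are.
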